5.7.3 Dispensing of Study Drug

Regular study drug reconciliation will be performed to document drug assigned, drug dispensed, drug returns, and drug remaining. This reconciliation will be logged on the drug reconciliation form and signed and dated by the study team.

5.7.4 Return or Destruction of Study Drug

At the completion of the study, there will be a final reconciliation of drug shipped, drug dispensed, drug returns, and drug remaining. This reconciliation will be logged on the drug reconciliation form, signed and dated. Any discrepancies noted will be documented and investigated, prior to return or destruction of unused study drug. Drug destroyed on site will be documented in the study files.

6 Study Procedures

6.1 Visit 1

Screening visit:

During this visit, we will do some tests and procedures to see if subjects are eligible to take part in this research study. The study staff will review the results of these tests and procedures. If subjects aren't eligible, the Principal Investigator will tell them why. At this visit we will:

- Ask about medical history
- Perform a physical exam, including height, weight, and "vital signs" (blood pressure, temperature, heart and breathing rates)
- Perform a chest x-ray
- Draw a blood sample
- Lab evaluation of CMP, CBC, Lipid Panel, CPK, TB, and Coccidiomycosis
- We may take swabs to test for certain fungal and bacterial infections
- Complete serum pregnancy if female subject is able to become pregnant

6.2 Visit 2

Day 0 Visit we will:

- Perform a physical exam, check vital signs and ask about side effects or health problems since last visit
- Exam scalp lesions to note any changes
- Take photographs of scalp lesions to document any changes
- Draw blood sample(s)
- Lab evaluation of CMP, CBC, Lipid Panel, and CPK
- Perform skin biopsy (one, 4-6 mm punch biopsy)
- Dispense study drug
- Complete serum pregnancy if female subject is able to become pregnant
- LLPAI
- DLQI
- PGA
- VAS
- VRS
- NRS
- Skindex-16

6.3 Visit 3

Week 2 Visit we will:

- Perform a physical exam, check vital signs and ask about side effects or health problems since last visit
- Exam skin lesions to note any changes
- Take photographs of skin lesions to document any changes
- Draw blood sample(s)
- Lab evaluation of CMP, CBC, Lipid Panel, and CPK
- Dispense study drug
- Adverse events assessment

- LLPAI
- DLQI
- PGA
- VAS
- VRS
- NRS
- Skindex-16

6.4 Visit 4

Week 4 Visit we will:

- Perform a physical exam, check vital signs and ask about side effects or health problems since last visit
- Exam skin lesions to note any changes
- Take photographs of skin lesions to document any changes
- Draw a blood sample
- Lab evaluation of CMP, CBC, Lipid Panel, and CPK
- Perform skin biopsy (one, 4-6 mm punch biopsy)
- Dispense study drug
- Serum pregnancy test if female subject is able to become pregnant
- Adverse event assessment
- LLPAI
- DLQI
- PGA
- VAS
- VRS
- NRS
- Skindex-16

6.5 Visit 5

Week 8 Visit we will:

- Perform a physical exam, check vital signs and ask about side effects or health problems since last visit
- Exam skin lesions to note any changes
- Take photographs of skin lesions to document any changes
- Draw a blood sample
- Lab evaluation of CMP, CBC, Lipid Panel, and CPK
- Dispense study drug
- Complete serum pregnancy if female subject is able to become pregnant
- Adverse events assessment
- LLPAI
- DLQI
- PGA
- VAS
- VRS
- NRS
- Skindex-16

6.6 Visit 6

Week 12 Visit we will:

- Perform a physical exam, check vital signs and ask about side effects or health problems since last visit
- Exam skin lesions to note any changes
- Take photographs of skin lesions to document any changes
- Draw a blood sample
- Lab evaluation of CMP, CBC, Lipid Panel, and CPK
- Dispense study drug
- Complete serum pregnancy if female subject is able to become pregnant
- Adverse events assessment
- LLPAI
- DLQI
- PGA
- VAS
- VRS
- NRS
- Skindex-16

6.7 Visit 7

Week 16 Visit we will:

- Perform a physical exam, check vital signs and ask about side effects or health problems since last visit
- Exam skin lesions to note any changes
- Take photographs of skin lesions to document any changes
- Draw a blood sample
- Lab evaluation of CMP, CBC, Lipid Panel, and CPK
- Dispense study drug
- Complete serum pregnancy if female subject is able to become pregnant
- Adverse events assessment
- LLPAI
- DLQI
- PGA
- VAS
- VRS
- NRS
- Skindex-16

6.8 Visit 8

Week 20 Visit we will:

Perform a physical exam, check vital signs and ask about side effects or health

- problems since last visit
- Exam skin lesions to note any changes
- Take photographs of skin lesions to document any changes
- Draw a blood sample
- Lab evaluation of CMP, CBC, Lipid Panel, and CPK
- Dispense study drug
- Complete serum pregnancy if female subject is able to become pregnant
- Adverse events assessment
- LLPAI
- DLQI
- PGA
- VAS
- VRS
- NRS
- Skindex-16

6.9 Visit 9

Week 24 Visit we will:

- Perform a physical exam, check vital signs and ask about side effects or health problems since last visit
- Exam skin lesions to note any changes
- Take photographs of skin lesions to document any changes
- Draw a blood sample
- Lab evaluation of CMP, CBC, Lipid Panel, and CPK
- Complete serum pregnancy if female subject is able to become pregnant
- Adverse events assessment
- LLPAI
- DLQI
- PGA
- VAS
- VRS
- NRS
- Skindex-16

6.10 Visit 10

Week 28 Visit we will:

- Perform a physical exam, check vital signs and ask about side effects or health problems since last visit
- Exam skin lesions to note any changes
- Take photographs of skin lesions to document any changes
- Draw a blood sample
- Lab evaluation of CMP, CBC, Lipid Panel, and CPK
- Complete serum pregnancy if female subject is able to become pregnant
- Adverse events assessment

- LLPAI
- DLQI
- PGA
- VAS
- VRS
- NRS
- Skindex-16

7 Statistical Plan

7.1 Sample Size Determination

Data analysis: Due to the costs associated with a study, we propose a single armed study of 22 LPP subjects, for a total of 22 subjects with corollary science including RNA sequencing. This will reduce costs and provide biomarkers predictive of response. Effect sizes will be estimated for the appropriate statistical tests that will be used for group comparisons in future studies. This will enable more accurate power and sample size estimates moving forward.

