	8.1 SAMPLE SIZE DETERMINATION	
	8.2 STATISTICAL METHODS	26

8.	3 SUBJECT POPULATION(S) FOR ANALYSIS	27
9	SAFETY AND ADVERSE EVENTS	28
9.	1 Definitions	28
9.		
9.	3 REPORTING OF SERIOUS ADVERSE EVENTS AND UNANTICIPATED PROBLEMS	32
	9.3.1 Sponsor-Investigator reporting: notifying the Mayo IRB	32
	9.3.2 Sponsor-Investigator reporting: Notifying the FDA and Funding Sponsor	35
9.	4 STOPPING RULES	36
9.	5 MEDICAL MONITORING	37
10	DATA HANDLING AND RECORD KEEPING	38
10).1 Confidentiality	38
10	0.2 SOURCE DOCUMENTS	38
10	0.3 CASE REPORT FORMS	38
10	0.4 RECORDS RETENTION	39
11	STUDY MONITORING, AUDITING, AND INSPECTING	39
11	1.1 Study Monitoring Plan	39
1 1	1.2 AUDITING AND INSPECTING	39
12	ETHICAL CONSIDERATIONS	39
13	STUDY FINANCES	40
13	3.1 Funding Source	40
13	3.2 SUBJECT STIPENDS OR PAYMENTS	40
14	PUBLICATION PLAN	40
15	REFERENCES	40
16	ATTACHMENTS	42
	Pruritus Visual Analogue Scale	43

List of Abbreviations

LIST OF ABBREVIATIONS

AE Adverse Event/Adverse Experience

BSA Body Surface Area

mCAILS Modified Clinical Assessment Scale of Severity for Index Lesion

Signs & Symptoms

CFR Code of Federal Regulations

CRF Case Report Form
CXCR3 Chemokine Receptor-3
CXCL9 Chemokines Ligands 9

DEGs Differentially Expressed Genes

Data and Safety Monitoring Board

DSMB

FDA Food and Drug Administration

GCP Good Clinical Practice
GVHD Graft Versus Host Disease

HIPAA Health Insurance Portability and Accountability Act

IB Investigator's Brochure

IL-1 Interleukin-1

IND Investigational New Drug Application

IFNα Interferon Alpha IFNγ Interferon Gamma

IRB Institutional Review Board

JAK Janus Kinase LP Lichen Planus

LPPAI Lichen Planopilaris Activity Index

LTR Lichenoid Tissue Reaction
MDC Myeloid Dendritic Cells
NRS Numerical Rating Scale
PDC Plasmacytoid Dendritic Cells
PGA Physician Global Assessment
PHI Protected Health Information

PI Principal Investigator

SAE Serious Adverse Event/Serious Adverse Experience

SOP Standard Operating Procedure

VAS Visual Analogue Score VRS Visual Rating Score

Study Summary

Title	Deucravacitinib (BMS-986165) in the Treatment of Lichen Planopilaris					
Running Title	Deucravacitinib (BMS-986165) in LPP					
Protocol Number	Version 1.6					
Phase	2					
Methodology	Open-Label, Single Arm					
Overall Study Duration	28 weeks					
Subject Participation Duration	Up to 28 weeks					
Single or Multi-Site	Single institution (MCA and MCF participating)					

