Objectives	To evaluate the safety and efficacy of Deucravacitinib (BMS-986165) in Lichen Planopilaris and Frontal Fibrosing Alopecia as assessed by the change in Physician Global Assessment (PGA) of skin, oral mucosa, and hair, LPPAI. To predict responses through the identification of unique biomarkers of LPP at week 0 and utilizing bulk, spatial, and single-cell RNA sequencing					
Number of Subjects	22 (12 in cohort A and 10 in cohort B)					
Diagnosis and Main Inclusion Criteria	Adult patients with active LPP 1) 18 years old or older at time of consent 2) Biopsy proven diagnosis of LPP					
Study Product, Dose, Route, Regimen	Deucravacitinib (BMS-986165) 6 mg orally administrated, twice daily (Cohort A) and 6 mg orally QD (Cohort B).					
Duration of Administration	Drug will be administered from Day 0 through Week 24.					
Reference therapy	None					
Statistical Methodology	The statistical analysis will provide descriptive summary statistics for categorical and continuous outcomes. Categorical variables will be described by their count and proportion of occurrence while continuous, normally distributed variables will be described by their mean and standard deviation; and continuous, non-normally distributed variables will be described by their median and range.					

1 Introduction

This document is a protocol for a human research study. This study will be carried out in accordance with the applicable United States government regulations and Mayo Clinic research policies and procedures.

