Lichen Planopilaris (LPP) is a form of lymphocyte-mediated scarring alopecia. It presents as discrete patches with characteristic perifollicular erythema and scale involving the scalp. LPP is histopathologically characterized by lichenoid inflammation at the infundibular portion of hair follicle. Cell-mediated cytotoxicity is the main pathogenetic mechanism in lichenoid tissue reactions and the maintenance and progression of chronic cytotoxic inflammation requires IFN gamma signaling. Disease progression results in permanent alopecia and is associated with negative quality of life impacts including depression and anxiety. There are no on-label or effective remittive treatments. Conventional topical (e.g. corticosteroids) and systemic immunosuppressives (e.g. mycophenolate mofetil) used in the treatment of LPP directly inhibit lymphocytes but generally cannot induce clinical remission ³. Therefore, there remains a critical unmet need for alternative therapeutic options to treat LPP.

Cutaneous LP is characterized by Type I and Type II IFN driven cell mediated cytotoxic immune response that is highly responsive to JAK1, 2 inhibitions ⁴⁻⁶. However, unlike LP, LPP is a chronic, scarring condition. The etiology of LPP as well as the scarring is poorly understood; however, Th17 cells are thought to play a critical role in this process. In line with the role of Type I & II IFNs and Th17 cells in LPP, more moderate responses are seen with to JAK 1, 2 inhibition ^{7 8,9}. Taken together, we believe that TYK2 inhibition has the potential to treat the inflammation of LPP as well as the scarring generated by Th17 stimulated fibroblasts.

We additionally propose a multi-center, exploratory, open-label, single-arm design study using Deucravacitinib (BMS-986165, systemic TYK2 inhibitor for the treatment of LPP with 6 mg orally QD (Cohort B) to assess safety and efficacy.

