Single cell RNA sequencing will be performed at week 0 and week 4 (Cohort A only). A total of up to 30 (14 pre-treatment, 14 post treatment, 4 controls) skin samples will be completed for single cell sequencing (Cohort A only). Bulk RNA sequencing will be completed on up to 30 tissue samples (14 pre-treatment, 14 post treatment, 4 healthy controls) (Cohort A only). Spatial RNA sequencing will be completed on 28 tissue samples (14 pre-treatment, 14 post treatment) (Cohort A only).

Bulk, single-cell and spatial RNA Transcriptome Sequencing: Samples will be prepped and analyzed per bulk, spatial, and single-cell RNA sequencing standard operating procedures of the University of Michigan genomics lab (Cohort A only). Processing and operating protocols are as follows:

Bulk, Single Cell and Spacial RNA Sequencing

Biopsy Processing for bulk and spatial sequencing:

Biopsies will be collected following standard Mayo BAP procedures. Immediately following collection, tissue biopsies will be submerged in formalin. Formalin samples will be shipped to the University of Michigan.

Biopsy Processing for single cell sequencing:

Biopsies will be collected following standard Mayo BAP procedures. Immediately following collection, tissue biopsies will be submerged and frozen in Cryostor CS10 media at a rate of -1°C/minute and stored at -80C. Frozen samples will be shipped within 2 weeks of collection to the University of Michigan. Upon receipt, samples will be stored at -80C until time of processing for single cell sequencing.

Single Cell Sequencing:

Cells will be isolated from cutaneous punch biopsies using collagenase or trypsin containing DNase. Epidermis and dermis are first isolated from one another and then processed separately. Cell quality and quantity will be assessed using Trypan Blue exclusion. Samples with >75% viability will be sequenced without additional cleanup steps. Samples with <75% viability will be further processed to increase concentration of viable cells prior to sequencing.

Primary and Secondary Measures:

All efficacy assessments will be performed prior to the administration of study treatment at each visit. The recommended order and the overall outline of measurements for the efficacy assessments are described below.

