7.2 Statistical Methods

Descriptive Statistics

Sample Size Computation and Power Analysis:

The sample size for this pilot study is set at 22 subjects for logistical and financial reasons. This is similar in size to other exploratory studies and will provide adequate data for estimation purposes for planning future studies. With 22 subjects, the study is intended to be for estimation purposes only.

Statistical Analysis Plan:

Data Analysis - The statistical analysis will provide descriptive summary statistics for categorical and continuous outcomes. Categorical variables will be described by their count and proportion of occurrence while continuous, normally distributed variables will be described by their mean and standard deviation; and continuous, non-normally distributed variables will be described by their median and range. The paired or unpaired Wilcoxon tests will be used to quantify differences in numerical outcomes while the McNemar's or Bowker's tests will be used to quantify changes in categorical variables. Complete response rate and complete/partial response rate and their corresponding 95% confidence intervals will be calculated and estimated using exact binomial method. Spaghetti plots will be used to visualize trend of the LPPAI score, PGA score, and Dermatology-QLI score at each time points for each individual. Effect sizes will be estimated for the appropriate statistical tests that will be used for group comparisons in future studies. This will enable more accurate power and sample size estimates moving forward.

Bioinformatic Analysis:

Bulk, Spatial, and Single-cell RNA Seq analysis: will be performed according to standard operating procedures of Mayo Clinic and University of Michigan genomics lab and bioinformatics. We will perform bulk, single cell and spatial sequencing pre and post therapeutically on tissue. Using these genomic techniques, we can determine differences within samples as well as between diseases in as few as 1-3 samples. Larger sample sizes will allow for confirmation of findings.

We will use bulk RNA sequencing to identify the enriched pathways of LPP and the pathway changes associated with treatment response. We will also define the single cell composition of LPP. We will examine the changes

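### Section 7.1 promises biomarkers predictive of response, but tissue sequencing in one small, fully treated cohort, with no stated error control or test in other subjects, can only yield candidate markers

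*Combined protocol and SAP*

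**What the plan says.** Section 7.1 gives cost as the reason for a single-arm study of 22 subjects with RNA sequencing, and then states what this buys: "This will reduce costs and provide biomarkers predictive of response". The objectives in the Study Summary say the same: "To predict responses through the identification of unique biomarkers of LPP at week 0". Section 7.2 confirms that the size was not calculated: "The sample size for this pilot study is set at 22 subjects for logistical and financial reasons".

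The Study Summary describes the design as "Open-Label, Single Arm", with no reference therapy, and the cohorts as "22 (12 in cohort A and 10 in cohort B"). Section 3.1 limits each tissue sequencing method to Cohort A. For single-cell work: "Single cell RNA sequencing will be performed at week 0 and week 4 (Cohort A only"). For bulk work: "Bulk RNA sequencing will be completed on up to 30 tissue samples (14 pre-treatment, 14 post treatment, 4 healthy controls) (Cohort A only").

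The bioinformatic part of Section 7.2 refers to the laboratories' standard operating procedures. It plans pathway changes and cell sub-population changes that go with response, and it validates the single-cell and spatial findings by bulk sequencing and immunohistochemistry. It states no false-discovery rule, cross-validation or hold-out set. It also says that these techniques can show differences in as few as one to three samples, and that larger samples will allow confirmation.

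**The concern.** Three things are needed before a week-0 marker can be called predictive of response to a drug: a comparison that separates drug effect from natural course, control of chance findings across many candidates, and a test in subjects who did not suggest the marker. The written plan has none of them.

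- **Comparison.** Every subject with an outcome receives deucravacitinib. The archival normal-scalp samples from the outside biobank carry no treatment outcome. Someone whose disease was mild, or would have settled anyway, looks the same as someone helped by the drug.
- **Chance findings.** The number of measured genes far exceeds the number of subjects, so some genes will line up with outcome by luck.
- **Outside test.** A second assay can show that a gene was measured correctly. It does not show that the gene predicts outcome, and the bulk sequencing is itself confined to Cohort A.

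At stake is what may be concluded. The study is meant to inform later trials, and a marker reported as predictive would carry more weight than these data can give it.

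**Working it through.** **The plan's own figure.** 12 + 10 = 22, which agrees. There is no power calculation to reproduce.

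**Inputs from the documents.** Cohort A has 12 subjects (Study Summary). Response means an LPPAI reduction of at least 25% at week 24, complete and partial combined (Sections 2 and 3.4). Withdrawn subjects are not replaced (Section 4.4.1). Section 3.1 lists 14 pre-treatment samples for a cohort of 12, and for bulk and single-cell work its parts add to 14 + 14 + 4 = 32 against a stated ceiling of 30.

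**Assumption.** The documents give no gene count. I take 20,000 and show 5,000 as well.

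**Formula.** Take a gene unrelated to outcome, with no ties. The chance that it ranks all k responders above, or all below, the n − k non-responders is 2/C(n,k). The expected number of such genes among G is G × 2/C(n,k).

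| Subjects, split | 2/C(n,k) | G = 5,000 | G = 20,000 |
|---|---|---|---|
| 12, 6:6 | 2/924 = 0.00216 | 11 | 43 |
| 12, 8:4 | 2/495 = 0.00404 | 20 | 81 |
| 12, 9:3 | 2/220 = 0.00909 | 45 | 182 |
| 12, 10:2 | 2/66 = 0.0303 | 152 | 606 |
| 14, 7:7 | 2/3,432 = 0.00058 | 3 | 12 |
| 14, 10:4 | 2/1,001 = 0.0020 | 10 | 40 |

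The even split is the most favourable case. Section 1.1 reports improvement in early Cohort A results and the response threshold is only 25%, so an uneven split is plausible. If every subject responds, or none does, there is no contrast at all.

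**Spread.** The expectation does not depend on correlation between genes, but the spread does. A simulation of 200 replicates (12 subjects, 6:6, 20,000 genes) gave:

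- moderate correlation (half the variance shared through 10 factors): mean about 43, median about 34, 95% range 9 to 142;
- strong correlation (70% shared through 5 factors): mean about 42, median about 15, 95% range 0 to 242.

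**With error control.** If a rank test were used at 8:4, the smallest two-sided p is 0.00404. A Benjamini-Hochberg procedure at 5% would then need at least 0.00404 × 20,000 / 0.05 = 1,616.2, that is 1,617 genes, at that minimum before it declared any. Depending on the error rule, a gene-level responder screen of this size could therefore return many chance genes or none.

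**The case against.** The case for leaving the plan alone has real weight.

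- **The aim is exploratory.** Sections 2 and 3.1 label it so, and Section 7.2 calls the study one for estimation and defers confirmation to larger samples. This stands, and it lowers the severity. It does not qualify the flat promise in Section 7.1, with which it conflicts.
- **The plan never describes a gene-by-gene responder screen.** Section 7.2 speaks of pathways and cell populations, and it names Wilcoxon tests only for the clinical outcomes. This stands too. The counts above are conditional on such a screen, and the 1,617 figure on a rank test.
- **The cited operating procedures may contain a false-discovery rule.** They may; they are not in the documents. They could not supply a control group or independent subjects.
- **The lack of a control is openly declared.** True, and a single-arm pilot is legitimate. The difficulty is the claim made for it.

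A reader might go further in three ways that the documents do not support. One is that reported markers would be mostly chance. That depends on how many true signals exist, which is unknown. Another is that no other subjects could ever test a marker. Section 3.1 takes a scalp biopsy from all subjects, and Table 3 banks Day 0 tissue and blood without a cohort limit, so Cohort B may hold usable samples. The plan does not assign them to this purpose, and those subjects are treated too, at the other dose. The third is that false markers will steer patient selection. The stated next use is power and sample-size planning.

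**Conclusion.** The point holds as a mismatch between claim and design. Section 7.1 attributes to the study a property that it lacks: tissue sequencing covers one treated cohort of about 12, predictive and prognostic value cannot be separated, and no error control or out-of-subject test is stated.

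The size of the chance problem is conditional. With unadjusted gene-level screening, 12 subjects and 20,000 null genes, about 43 to 182 perfect separators are expected for splits from 6:6 to 9:3. Fewer genes or 14 subjects bring the best case down to about a dozen or below, and correlation makes any single realisation uncertain. The lack of a comparator does not depend on any of these assumptions.

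Severity is low to moderate. No primary endpoint or safety rule depends on this aim, but it limits what may be concluded from it.

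**What to change.** 1. In Section 7.1, replace the sentence with: *will generate candidate week-0 markers associated with LPPAI change; predictive and prognostic value cannot be separated, and confirmation in independent subjects is needed.* Align the matching objective in the Study Summary.
2. Make the main week-0 analysis a short, pre-named list of pathway scores from the pathways that Sections 1.1 and 1.2 already name (type I interferon, interferon gamma, IL-12, IL-23/Th17). Relate each score to continuous percent LPPAI change at week 24 by rank correlation with a 95% confidence interval. This avoids dependence on the responder split. The intervals will be wide, and that should be visible.
3. Report any gene-level screen only with false-discovery control and leave-one-subject-out error, and write the rule into Section 7.2 rather than leaving it to procedures outside the protocol.
4. Reconcile the 12 subjects in Cohort A with the 14 pre-treatment samples in Section 3.1, and the parts adding to 32 with the ceiling of 30. If banked Cohort B material is meant to serve as a later test set, say so.

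The cost is protocol and SAP wording plus a few analyses of data already planned, with no extra subjects, samples or visits. The downside is a less ambitious claim.
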